4.1 IDENTIFYING PARTICIPANTS

At the commencement of the study, the care team will approach pregnant women who meet the criteria. Patients will get a Participant Information Sheet (PIS) and can reach out to the study team if they wish to participate. Each participant is only required to attend a single visit, which will last roughly 1 hour.

 Pregnant volunteers will be recruited at their first (10-12 week) and second (20 weeks) scans in line with their clinical care. In addition to their clinical ultrasounds, an ophthalmic and carotid artery ultrasound will be conducted. In addition a retinal scan and blood sample taken.

Potential subjects will be identified by the care team in the following clinics

- Hypertension Clinic (Recruitment will be overseen by [name](UoD/NHS))
- IVF clinic (Recruitment will be overseen [name] [name] (UoD/NHS))

 Obstetric Antenatal Clinics (Recruitment will be overseen [name] [name] (UoD/NHS) and [name] (NHS))

Advertising of the study in gyn clinics via posters adverts to invite subjects to volunteer by contacting the study team.

Potential subjects will be invited during their clinic visit and provided with a Participant Information Sheet (PIS), which includes details on how to contact the study team if they wish to participate. Additionally, interested participants will be contacted via a short telephone call or email to screen them for the inclusion/exclusion criteria.

4.2 CONSENTING PARTICIPANTS

The study team will consent the participants and ensure they have a minimum of 24h from receiving the PIS before requesting consent.

Consent Process: Consent will be obtained from each participant group prior to the start of the study. Participants will have the option to provide consent either electronically via email before the examination day or in person at the examination room immediately prior to the examination. A digital or hard record of consent will be kept securely in Cardiovascular Research Offices. During consent it will be made clear how the participants can withdraw from the study and their rights regarding the data, highlighting the information on the PIS.

Where a participant requests to speak with a physician from the study team the consent process will not be completed until the participant has spoken to the physician and had all their questions answered to their satisfaction.

The informed consent process will be conducted in compliance with TASC SOP07: Obtaining Informed Consent from Potential Participants in Clinical Research

4.3 SCREENING FOR ELIGIBILITY

The consenting of participants from the groups will be performed by the CI, PI or GCP trained delegated members of the study team competent in obtaining consent for research purposes.

4.4 INELIGIBLE AND NON-RECRUITED PARTICIPANTS

The reason(s) for ineligibility will be explained to participants and any questions they have will be answered. They will be thanked for their participation in screening.

4.5 WITHDRAWAL PROCEDURES

Participants are free to withdraw from the study at any time. If at any time the participant formally withdraws her consent for future participation and disclosure of future information, no further evaluations will be performed, and no additional data should be collected. Data collected before withdrawal will be retained and used in the study analysis, unless the participant requests

otherwise. If participants withdraw during the visit, they will have the option to request that data already collected is not to be used in the study.

5 DATA COLLECTION & MANAGEMENT

Data management will adhere to the Tayside Academic Sciences Centre Standard Operating Procedures (TASC SOPs) on Data Management, specifically focusing on Data Management Systems in Clinical Research. The data management system (DMS) will utilize EXCEL and align with the study protocol, Case Record Form (CRF), and investigators' specific needs. The CRF will gather essential information to fulfill the study objectives and ensure participant eligibility and safety. Maintaining medical confidentiality and data protection laws, the database management follows relevant guidelines. The University of Dundee acts as the Data Controller, with the Chief Investigator (CI) serving as the Data Custodian. While the CI can delegate CRF tasks, they are accountable for the completeness, accuracy, and coherence of the CRF. Any issues or questions will be addressed by the CI or a designated member of the research team.

5.1 DATA COLLECTION

The patients will be given an identification number to ensure anonymity. Data collected will include age, previous medical history, medications, diagnosis, treatment, blood report findings, and personal history. This clinical data will be used in the analysis of results and will be used to correlate with the findings of the CV assessments. The data will be collected by the research team on a paper Case Record Form (CRF), which will not hold any name, initials, and CHI, with subsequent transcription into an Excel database. Electronic storage will be in an encrypted form on a University of Dundee password-protected device. Study assessments will be conducted by the PI and a trained research member of the team under the supervision of the CI.

On the same day as the blood sample, carotid artery doppler, and retinal imaging, an ophthalmic artery Doppler will be conducted. In the unlikely event that this is not possible, the ophthalmic artery doppler will be finished in 7 days.

5.2 DATA MANAGEMENT SYSTEM

Data management will be conducted in compliance with TASC SOPs on Data Management, Data Management Systems in Clinical Research. The data management system (DMS) will be EXCEL. The DMS will be based on the protocol and CRF for the study and individual requirements of the investigators. The CRF will collect only information that is required to meet the aims of the study and to ensure the eligibility and safety of the participant. The database is managed in line with all applicable principles of medical confidentiality and data laws. The Data Controller will be the University of Dundee and the Data Custodian will be the CI. The CI may delegate CRF completion but is responsible for completeness, plausibility, and consistency of the CRF. Any queries will be resolved by the CI or delegated member of the study team.

Security measures and	Data will be stored n University of Dundee one
other mechanisms to	drive which is safe and protected by UoD-IT.
protect personal data	Data in the paper files will be locked in a secure
	cabinet in the Cardiovascular Medicine
	division.

Only members of the study group (~4 people) will have access to the files. Caldicott approval will be sought for the principle investigator and Chief Scientist.

6 STATISTICS AND DATA ANALYSIS

Descriptive statistics will be used in this study. To compare between groups, we will use a t-test and binary logistic regression, depending on the situation. Logistic regression analysis will be conducted to evaluate and account for any confounding factors. In order to validate the non-invasive techniques, a Bland-Altman analysis will be conducted to evaluate the comparability of the methods. Regression analysis to identify predictors of pregnancy outcomes. The Statistical analysis will be performed in SPSS (SPSS Statistics. 2022. Version 29.0.0.0. International Business Machines Corporation, New York, United States).

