3 STUDY DESIGN

The study design is a prospective study, as it examines endothelial function in pregnant women and see how this relates to the potential development of gestational hypertension.

Study Aim: Imaging the retina in mid-stages of gestation and tracking pregnancy outcomes in correlation with serum biomarkers and for standard diagnostic measurement (ultrasound pulse-wave Doppler) imaging.

 Pregnant women will be recruited at the normal pre-natal visits (early and mid gestation scans)

- Blood samples will be taken in addition to bloods take in line with routine care (early 10-12 week scan). 20-week scan women will be requested to provide blood samples. (sFlt-1 &PLGF (clinically used to diagnose PE), endothelin-1 (marker of endothelial dysfunction))
 - Recruit women who are pregnant and follow pregnancy outcome
 - Recruit women who have gestational hypertensionGH and gestational-matched normal tensive women for CV assessment.
 - Endothelial CV assessment.
 - Retinal imaging
 - Blood sample (sFlt-1 &PLGF (clinically used to diagnose PE), endothelin-1 (marker of endothelial dysfunction))
 - Ultrasound
 - Carotid
 - Ophthalmic artery doppler

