3.2 STUDY RECRUITMENT

Women will be recruited who are pregnant for assessment in mid and/or late term. The outcome of the pregnancy will be tracked.

Women will be invited to join the study by the care teams in clinics at Ninewells and the Tayside area

- Obstetric Antenatal Clinics (Recruitment will be overseen [name] [name] (UoD/NHS) and [name] (NHS))
- Assisted conception clinic (Recruitment will be overseen [name] [name] (UoD/NHS))
- Hypertension Clinic (Recruitment will be overseen by [name](UoD/NHS))

This is a prospective study. Control groups will be made up of women that do not get gestational hypertension. Pregnant women that attend the Hypertension clinic may be recruited due to their gestational hypertension. Women attending the Obstetric Antenatal Clinics and Assisted conception clinics will be identified with clinical collaborators including [name] [name], [name] and [name]. To be able to identify potential participants from their medical records Caldicott Approval will be sought. Only with Caldicott approval will the medical records be searched.

The care team will approach or invite participation in the study in clinic. Any invitation will introduce the potential patient to the study team and will include a PIS. The care team will not follow up with patients to determine their interest in the study.

The study team will include Clinical Research Centre nurses that will assist with recruitment. The study team will confirm recruitment via a short telephone conversation prior to them attending Ninewells for the study visit.

Advertisement of the study and identification of potential participants will be identified from the NHS Tayside clinics at Ninewells Hospital including maternity clinics, ultrasound department, antenatal clinics, day assessment unit, Assisted Conception Unit, https://www.acudundee.org/ hypertension and diabetics clinics among others. Caldicott approval will be gained to allow identification of potential participants from medical records and clinical lists by the care team. Letters with PIS may be sent to the potential participants from the clinical team. We chose the following sites, since this is where pregnant women obtain their routine care.

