3.12 STUDY POPULATION

Our study populations are defined as follows

The study design is prospective study. All pregnant women will be included at the start except for exclusion criteria see (3.15). Outcome of pregnancy will be documented and participants will be placed into one of two groups retrospectively:

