6.1 SAMPLE SIZE CALCULATION

Comparison of CV function in women at high and low risk of PE

Ninewells has approximately 4500 births per year with approximately 450 cases of gestational hypertension. Our goal here is to describe the evolution of maternal microvascular function in women that develop gestational hypertension comparing to those that do not develop gestational hypertension.

Our previously published studies (Khan et al 2005 Hypertension, https://doi.org/10.1161/01.HYP.0000186328.90667.95; Changes in Endothelial function preceded the clinical disease in women in whom PE develops) demonstrated changes in microvasculature at 26 weeks in n=15 women with PE compared to normotensive (n=54). Using this previous data, a Power Analysis (G*power)) -A Piori carried out to compute the required sample size for the Wilcoxon-Mann Whitney test (2 groups). With

αα

= 0.05 and power of 95% to detect an effect size of 25%, each group requires a n=11.

As this is a prospective study to obtain measurements at the onset of gestational hypertension, we predict we need to recruit 110 women to obtain the 10% of women that develop gestational hypertension. Women who are high-risk or that have been newly diagnosed, i.e. attending hypertensive clinics, will be recruited

Further details:

 During-Pregnancy: Recruit 110 women to account for the 10% who will develop gestational hypertension.

Sample size required for each group (high vs. low risk):11 women per group

• Total Participants:

-During-Pregnancy: 110 women (recruitment to achieve the final sample of 22 women)

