6.2 PROPOSED ANALYSES

- **Study
- **Aim**: To investigate correlations between retinal imaging, ultrasound and blood sample biomarkers and future CVD risk factors in mid-late stages of gestation.
 - Hypothesis:

Cardiovascular Assessment:

Blood biomarker (sFlt-1, PIGF)) will correlate with retinal vascular changes and Dopple rultrasound indices, potentially predicting future CVD.

- **Methods**:
- Perform *correlational analysis* between retinal metrics and blood biomarkers to examine associations.
- Conduct *logistic regression analyses* to assess whether retinal imaging metrics in early pregnancy predict future CVD risk.
- *Multivariable regression modeling* to control for confounding factors such as maternal age, BMI, and pre-existing health conditions.

Data Protection Impact Assessment (DPIA)

- We aim to understand the link between retinal imaging biomarkers and cardiovascular function in gestational hypertension, predicting CVD risk factors and informing early interventions.

What will be the effect on data subjects?

-Positive Impact**: Early detection of risk factors for cardiovascular health, potentially improving maternal health management and long-term care.

What is the nature of the University's relationship with the data subjects?

- The University serves as the primary researcher and data controller, conducting the study with informed consent from participants. The relationship is one of informed, voluntary participation in medical research.

Are they expecting you to use their data in the way you've proposed?

- Yes, participants are fully informed through the consent process about the study's objectives, data collection, and how their data will be used for research on maternal and cardiovascular health.

Are there prior concerns with this proposed activity in the public domain that you are aware of?**

- Retinal imaging and biomarker studies in maternal health are generally well-accepted, though concerns about the use of sensitive medical data highlight the importance of rigorous data protection.

Is the University signed up to any codes of conduct in respect of the data processing?

- The University adheres to all GDPR guidelines and maintains compliance with institutional data protection policies, ensuring ethical handling and storage of sensitive health data.

Are there sufficient resources to meet the data security requirements for this type of processing?

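### Controls are called gestation-matched in one line, but group formation does not follow it and the between-group comparison does not name gestational age

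*Protocol*

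**What the plan says.** **Matching.** Section 3 (Study design) lists, among the design points: "Recruit women who have gestational hypertensionGH and gestational-matched normal tensive women for CV assessment". No ratio, gestational-age tolerance or pairing rule is given there or anywhere else.

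**Group formation.** Section 3.2 says "Control groups will be made up of women that do not get gestational hypertension". Section 3.12 says "Outcome of pregnancy will be documented and participants will be placed into one of two groups retrospectively". Neither mentions matching, and the control criteria in sections 3.14 and 3.15 contain no gestational condition. Section 6.1 recruits 110 women to reach a final sample of 22. It does not say how 11 controls are chosen from the 110 − 11 = 99 or so women without GH.

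**Analysis.** Section 6 says "To compare between groups, we will use a t-test and binary logistic regression, depending on the situation". Section 6.2 adds multivariable regression "to control for confounding factors such as maternal age, BMI, and pre-existing health conditions". Gestational age is not in that list, although the list is open-ended.

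**Sample size.** Section 6.1 sizes for a two-group Wilcoxon-Mann-Whitney test: with alpha "0.05 and power of 95% to detect an effect size of 25%, each group requires a n=11".

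**The concern.** Matching on gestation makes the two groups share their gestational-age distribution. Any part of a retinal, Doppler or biomarker measure that moves with gestation then cancels out of the difference in means. A two-sample t-test does not know this: it estimates its standard error from the full within-group spread, gestation included. Its intervals are too wide for the design, it rejects less often than 5% under the null, and it misses differences that the same scans could show.

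Gestation is likely to vary in this study. Section 3.5 accepts a single visit at either week 10 or week 20, each within 3 weeks, so scans may fall in weeks 7 to 13 or 17 to 23. Section 3.14 places cases in mid-to-late gestation. With 22 women analysed, a null result could partly reflect the choice of test.

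**Working it through.** **1. The plan's own figures.** 110 × 10% = 11 cases reproduces. The 11 per group does not follow if the 25% effect is read as a standardised difference of 0.25: n = 2 × (1.960 + 1.645)² / 0.25² ≈ 416 per group (two-sided), and about 437 with the usual Wilcoxon-Mann-Whitney efficiency of 0.955. Conversely, 11 per group with 95% power needs a difference of about 1.66 SD (two-sided). A 25% relative difference would match that if the coefficient of variation were 0.25 / 1.66 ≈ 15%, but the protocol gives no SD. The figure of 1.66 SD is used below as the effect the design implies.

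**2. Model.** Let the outcome have unit SD within each group and let rho be the share of its variance due to gestation:

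outcome = √rho × gestation + √(1 − rho) × error + d × (GH case)

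The protocol gives no rho, so a range of 0 to 0.6 is assumed.

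**3. Standard error under matching.** If each case and its control share gestational age, the variance of the difference in means is 2(1 − rho)/11. The t-test estimates 2/11. At rho = 0.4 the true standard error is √(2 × 0.6/11) = 0.330, while the t-test works with about √(2/11) = 0.426, which is 1.29 times too large.

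**4. Simulation, matched controls** (11 v 11, two-sided 0.05, 20,000 runs per setting). The adjusted model is a linear model on group plus gestational age.

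| rho | t-test type I error | Power at 0.8 SD: t-test v adjusted | Power at 1.66 SD: t-test v adjusted |
|---|---|---|---|
| 0 | about 5% | 43 v 43% | 96.0 v 95.9% |
| 0.2 | about 3% | 43 v 52% | 97.2 v 98.4% |
| 0.4 | about 1.6% | 42 v 63% | 98.5 v 99.8% |
| 0.6 | about 0.4% | 41 v 80% | 99.2 v 100% |

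The adjusted model holds its type I error close to 5% throughout. The 0.8 SD effect is an assumption, chosen to show what happens below the design effect.

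**5. Is individual pairing needed?** No. With frequency matching over two gestational windows and no pairs, the t-test's type I error is 3.2% (rho 0.2) and 1.6% (rho 0.4). Power at 0.8 SD is 42 v 51% and 41 v 63%.

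**6. No matching, gestation distributed alike in both groups.** The t-test now has its nominal error rate. Power at 0.8 SD, t-test v adjusted, is 43 v 49% (rho 0.2) and 44 v 62% (rho 0.4). At rho = 0 the adjusted model loses about 2 points.

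**7. Paired t-test.** It has 10 degrees of freedom, against 19 for the adjusted model. At rho = 0 and 0.8 SD its power is 39.9%, against 43.1% for the unpaired test. It becomes worthwhile only when rho exceeds about 0.1 to 0.2, and it needs real pairs.

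**The case against.** The strongest reply is that matching is not an established feature of this design. It rests on one undefined line, and sections 3.2 and 3.12 describe an outcome-defined cohort. If nothing is matched, the t-test is not conservative. Section 6 does not say that the t-test is the independent-samples version, a detail often left to a statistical analysis plan. The covariate list in 6.2 is open, and section 6 promises to account for any confounders. All of this stands, and it makes the loss conditional. It does not remove the point: the sections disagree on how controls arise, and the adjusted model is the better choice under either reading unless gestation explains almost nothing.

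The size is also open to challenge. Both rho and 0.8 SD are assumed, giving every pair identical gestation is the best case for matching, and at the effect the design implies the gain is about 1 point. That stands too.

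Three stronger readings are tempting but not supported:

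- A reader might infer that the study forfeits power bought by matching. Section 6.1 took no credit for matching, so nothing was bought.
- A reader might infer that the logistic regression also has over-wide error bars. Ignoring matching there mainly pulls the odds ratio towards the null, and nothing was computed for it.
- A reader might infer that a paired test is required. No passage shows individual pairing.

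If gestation differs systematically between the groups, the problem is bias rather than lost precision. That is a separate question, and the figures here do not address it.

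**Conclusion.** The point holds in conditional form. The protocol contradicts itself on whether controls are matched, and its stated comparison does not name the one factor it says it matches on. If matching happens, an unadjusted two-sample t-test errs on the conservative side: at 0.8 SD it gives up about 9 points of power at rho 0.2 and about 21 at rho 0.4. At about 1.66 SD the loss is roughly 1 point, so it matters mainly if true differences are smaller than the sample size presumes. Without matching, adjustment still gains at rho of 0.2 or more and costs about 2 points at rho 0. These sizes rest on an assumed rho, an assumed 0.8 SD effect and a linear effect of gestation. False positives are not inflated in any setting examined, so this is a worthwhile improvement rather than a fault that invalidates the comparison.

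**What to change.** - **Section 6:** make the between-group analysis a linear model of each retinal, Doppler and (log) biomarker measure on GH group plus gestational age at assessment, in place of the t-test.
- **Section 6.2:** add gestational age at assessment to the named covariates.
- **Section 5.1 and the CRF:** record gestational age at assessment, which the listed data items do not name.
- **Sections 3, 3.2 and 3.12:** reconcile whether controls are matched. If they are, state whether individually or by frequency, the tolerance, the ratio, and how 11 controls are drawn from the women without GH. If not, delete the reference to matching. Use a paired analysis only if matching is individual.

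The cost is a few sentences, one recorded item and one degree of freedom (19 instead of 20). If controls are unmatched and gestation explains nothing, power falls by about 2 points at 0.8 SD.

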6.1 SAMPLE SIZE CALCULATION

Comparison of CV function in women at high and low risk of PE

Ninewells has approximately 4500 births per year with approximately 450 cases of gestational hypertension. Our goal here is to describe the evolution of maternal microvascular function in women that develop gestational hypertension comparing to those that do not develop gestational hypertension.

Our previously published studies (Khan et al 2005 Hypertension, https://doi.org/10.1161/01.HYP.0000186328.90667.95; Changes in Endothelial function preceded the clinical disease in women in whom PE develops) demonstrated changes in microvasculature at 26 weeks in n=15 women with PE compared to normotensive (n=54). Using this previous data, a Power Analysis (G*power)) -A Piori carried out to compute the required sample size for the Wilcoxon-Mann Whitney test (2 groups). With

αα

= 0.05 and power of 95% to detect an effect size of 25%, each group requires a n=11.

As this is a prospective study to obtain measurements at the onset of gestational hypertension, we predict we need to recruit 110 women to obtain the 10% of women that develop gestational hypertension. Women who are high-risk or that have been newly diagnosed, i.e. attending hypertensive clinics, will be recruited

Further details:

 During-Pregnancy: Recruit 110 women to account for the 10% who will develop gestational hypertension.

Sample size required for each group (high vs. low risk):11 women per group

• Total Participants:

-During-Pregnancy: 110 women (recruitment to achieve the final sample of 22 women)

